### Efficacy Analyses

Summary statistics (e.g., means, standard deviations, frequencies, etc.) of the demographic characteristics and questionnaire responses will be calculated for each treatment group and applicable time points.

For the primary comparisons, the treatment groups will be compared using the analysis of covariance method with the response to “relieving the discomfort of dry mouth” from the modified PPAQ I as the response and DMI severity score, response to “how moist does your mouth feel right now” at baseline, or response to “how dry does your mouth feel right now” at baseline may be used as the covariates. Statistical comparisons will be one-sided with a significance level of 0.025.

$$Y_{i1} = \mu + \alpha \cdot Covariate_i + \beta \cdot Group_i + \epsilon_i$$

The secondary endpoints of interest will be the responses to “how moist does your mouth feel right now” and “how dry does your mouth feel right now” from the MD questionnaire immediately after use at Day 1. The Experimental rinse group will be compared to water using the analysis of covariance method with the immediate score as the response and DMI severity score and baseline response may be used as the covariates.

Responses to all other questions and time points will be of tertiary interest. Additional analyses of the data may be performed.

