## PROTOCOL BODY

### 1. Background

Xerostomia or dry mouth is a subjective sensation of oral dryness. It affects 5.5 to 46% of the adult population with higher prevalence in females and older people (however this condition is not related to age itself). The degree of xerostomia and salivary hypofunction do not always correlate with each other. Xerostomia may be caused by a variety of underlying etiologies, including systemic diseases (diabetes, cardiac disease, cancer and cancer treatments, rheumatoid arthritis, Alzheimer's disease, Parkinson's disease, HIV/AIDS, Sjögren's Syndrome, anemia), medications, head and neck radiation and modifiable lifestyle factors (smoking, sleep apnea, alcohol use etc.). Treatment of clinical symptoms of xerostomia can be divided into two categories: systemic sialagogues (pilocarpine and cevimeline) and topic agents like saliva substitutes, topical lubrication products, candies, chewing gum and water.

*Ref: Etiology, evaluation, and management of xerostomia Jillian W. Millsop, Elizabeth A. Wang, Nasim Fazel. Clinics in Dermatology. Volume 35, Issue 5, September–October 2017, Pages 468-476*

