#### Baseline/Day 1 (Visit 2)

Continuance criteria will be assessed. Subjects will have an Oral Examination at the site. Subjects will be randomly assigned to one of three treatment groups by a Balance & Assignment (B&A) program based on age and DMI severity score. Assigned treatment product kit boxes will be distributed and written instructions reviewed. In addition, all groups will be instructed to continue using the acclimation products per acclimation instructions. Subjects will be sent home with copies of questionnaires, their assigned kit box, the product diary, and the standardized snack. While at home, subjects will complete the Baseline MD questionnaire over the phone with site staff. Subjects will then use their assigned product for the first time and then a timer will be set for 6 hours. Immediately following the product use, subjects will complete the Immediate MD Questionnaire over the phone with site staff. Site staff will contact the subjects at home at the corresponding timepoints for completing the remaining questionnaires, (the PPAQ I/ MD 30-minute Questionnaire, the PPAQ I/ MD 1-hour, 2-hour, 4-hour and 6-hour Questionnaires).

Subjects will be instructed to refrain from eating, drinking, smoking, using their test products, using tobacco, using a medicated lozenge, chewing gum, or breath mints during the 6-hour test period. Subjects may consume their provided standardized snack immediately after the 4-hour questionnaire.

Should a subject not be able to follow the drinking or eating restrictions for the full six hours (i.e. require a rescue product such as water), the subject will be asked to fill out the next set of questionnaires, and then they will be allowed to resume normal activity for the rest of Day 1. Site staff will record the time the subject completed the questionnaires in General Comments. If desired, the subject will be allowed to remain in the study.

After the 6-hour questionnaire, subjects will be reminded to adhere to their assigned product use instruction sheet for the duration of the study. Subjects will be asked to complete the product diary tracking their product usage and water intake. Subjects from all groups will be allowed to sip water as needed on Days 2 – 7. Subjects will be reminded to bring their acclimation and treatment kit boxes and completed product diary to their next study visit.

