## 10. Method of Assigning Subjects to Treatment Groups

Study Design	n	n/group	B&A Program	PRA Block Size	Strata	Cut-offs*	Cohab
Parallel	150	50	Yes	3	DMI Severity Score; Age	Mild (2-5), Moderate (6-8), Severe (9-12); <=54, >54	Yes

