### B&A Program

At the Baseline visit, subjects will be randomly assigned to one of the three treatment groups (up to 50 per group) using an encoded B&A program supplied by the Sponsor. The subjects will be stratified based on DMI Severity Score and age. Subjects residing in the same household will be assigned to the same treatment group.

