## 11. Determination of Sample Size

Forty-five subjects per treatment group completing the study will ensure 80% power to detect a difference of at least 0.66 units on the 5-points PPAQ 1 scale in the Positive Control or Experimental rinse relative to water with a standard deviation of 1.1, in one-sided testing at a 2.5% significance level (based on published research). A target of up to 50 subjects will be recruited per group (total of up to 150) allowing for a 10% dropout rate.

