## 12. Efficacy Variables

### DMI Questionnaire

The following set of questions will be asked at the Acclimation (Visit 1).

(Severity Score = sum of 4 questions where: strongly disagree= -2, disagree= -1, disagree a little=0, agree a little=1, agree=2, strongly agree=3). Subjects to answer 2 or more of the 4 questions below positively in order to continue into the study. For summing the DMI score for randomization purposes, negative scores (strongly disagree= -2, disagree= -1) will be calculated as 0 in the database.

How much do you agree or disagree that you experience the following? (strongly disagree, disagree, disagree a little, agree a little, agree, strongly agree)

- 1) No moisture in the mouth
- 2) Lips sticking to teeth
- 3) Tongue sticking to roof of mouth
- 4) Throat feels dry

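### Allocation is stratified by DMI severity and age, but the primary ANCOVA leaves its covariates optional, so DMI may be omitted and age is in no model

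*Combined protocol and SAP*

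**What the plan says.** **Allocation.** Section 3, Baseline/Day 1 (Visit 2), assigns subjects by a Balance & Assignment "program based on age and DMI severity score". Section 10 repeats this, "The subjects will be stratified based on DMI Severity Score and age", and its table gives the cut-offs: "Mild (2-5), Moderate (6-8), Severe (9-12); <=54, >54". That makes 3 × 2 = 6 strata, with a block size of 3.

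**Primary model.** Section 15, Efficacy Analyses, prescribes analysis of covariance. It names three candidates joined by *or* (DMI severity score, baseline moistness, baseline dryness) and closes with "at baseline may be used as the covariates. Statistical comparisons will be one-sided with a significance level of 0.025". The formula carries one unnamed covariate term plus group. No rule says which candidate enters, how many, or who decides and when.

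**Secondary model.** The wording is tighter: "DMI severity score and baseline response may be used as the covariates". Two covariates are named and joined by *and*, so only the optional verb is left open. Age is again absent.

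**DMI scoring.** Section 12 scores each item from -2 to 3 and adds: "For summing the DMI score for randomization purposes, negative scores (strongly disagree= -2, disagree= -1) will be calculated as 0 in the database". Section 15 does not say which version of the score enters the model.

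No other section fixes the covariate set.

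**The concern.** A trial that balances its arms on two factors would normally carry both into the primary model. Otherwise the standard error ignores the balance that the design created. When the factor is prognostic, the test then rejects less often than its nominal level and some power is lost.

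The second issue is that Hypotheses 1 to 3 are tested in sequence at one-sided 0.025. Serial gatekeeping holds that level only if each step is a single test defined before unblinding. As worded, several models comply for each hypothesis.

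**Working it through.** **1. The plan's own figure.** Section 11 gives a difference of 0.66, SD 1.1, one-sided 0.025, and states "Forty-five subjects per treatment group completing the study will ensure 80% power to detect a difference of at least 0.66 units". The noncentrality is 0.66 / (1.1 × √(2/45)) = 2.846. On 88 degrees of freedom the noncentral t gives 80.4% power (79.5% with 44 per group). Recruitment is 45 / 0.90 = 50 per group. The stated size reproduces, and it assumes no gain from covariates.

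**2. Models that comply.** With at most one covariate: DMI, moistness, dryness, or none, which is four. If the plural *covariates* allows any subset of three: 2³ = 8. None contains age.

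**3. Which DMI score fits the strata.** Eligibility (Section 4) needs at least two of four items answered on the agree side, so at least two items score 1 or more.
- Negatives set to 0: minimum 1 + 1 + 0 + 0 = 2, maximum 4 × 3 = 12. This is exactly the 2–12 range in Section 10.
- Raw scores: minimum 1 + 1 - 2 - 2 = -2, which falls in no stratum.

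Only the zeroed score matches the randomisation.

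**4. Power.** The documents give no correlations and no age effect, so all of these are assumptions. Simulation settings: 135 subjects in three groups, permuted blocks of 3 within the six strata, even age split, total SD 1.1, true difference 0.66, moistness–dryness correlation 0.7, each correlated 0.3 with DMI. There were 40,000 runs per setting, and 20,000 in a separate run for the moistness-only column. Entries are power in %.

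| Correlation with outcome (DMI / MD item) | Age-group difference | No covariate | DMI | Moistness only | DMI + age | DMI + age + moistness |
|---|---|---|---|---|---|---|
| 0.2 / 0.35 | 0 | 81.2 | 82.4 | 85.1 | 82.3 | 85.5 |
| | 0.3 | 81.1 | 82.3 | 85.4 | 82.9 | 86.2 |
| | 0.6 | 81.7 | 82.8 | 86.3 | 84.9 | 88.1 |
| 0.3 / 0.5 | 0 | 81.4 | 84.1 | 90.6 | 84.1 | 91.0 |
| | 0.3 | 81.8 | 84.4 | 90.6 | 84.9 | 91.7 |
| | 0.6 | 82.2 | 84.9 | 90.7 | 86.8 | 93.7 |

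Reading across:
- Adding age to DMI gains about 0, 0.5 and 2 points at age differences of 0, 0.3 and 0.6 (for example 84.9 - 82.8 = 2.1).
- Moistness only, which Section 15 already permits, beats DMI + age in every row (for example 90.6 - 84.1 = 6.5, and 86.3 - 84.9 = 1.4).
- DMI + age + moistness exceeds moistness only by 0.4 to 3.0 points (85.5 - 85.1; 93.7 - 90.7). Gaps of about 0.4 are near simulation error.

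**5. Level of the unadjusted test.** At an age difference of 0.6, one-sided size is 1.8–1.9% with no covariate, 2.1% with DMI only and about 2.6% with DMI + age (nominal 2.5%).

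**6. Choice after unblinding.** Probability under the null, with no age effect, that the smallest one-sided p-value among the permitted models is below 0.025:

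| DMI / MD correlation | Best of four | Best of eight |
|---|---|---|
| 0.1 / 0.2 | 3.1% | 3.2% |
| 0.2 / 0.35 | 3.7% | 3.8% |
| 0.3 / 0.5 | 4.4% | 4.6% |

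A separate simulation with somewhat different assumed correlations gave 2.9–3.6% and 3.1–4.2%. About 3 to 4.5% is a fair summary.

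**The case against.** **The test remains valid.** A reader might infer that ignoring the strata biases the treatment effect or inflates the error rate. It does neither: step 5 shows size below 2.5%. This part of the objection stands in full.

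**Age may matter little.** Section 1 describes dry mouth "with higher prevalence in females and older people (however this condition is not related to age itself", and the documents give no age effect. With no age effect, adjusting for age gains nothing. It also costs next to nothing, and it aligns the analysis with the randomisation.

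**The no-covariate model is a strained reading.** Section 15 prescribes analysis of covariance and writes a covariate into its formula. The optional verb keeps the reading arguable, but the more realistic departure is an MD item used in place of DMI. Losses measured against the no-covariate model should not carry the argument.

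**The list is short and closed.** All three candidates are measured before first product use. A reader might infer that the sponsor intends to choose the best result after unblinding. No section says so, and the figures in step 6 apply only if it happened.

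**Why not simply DMI + age?** Because step 4 shows that this would be weaker than a model the plan already permits. The baseline MD call comes after assignment and kit distribution, which might suggest excluding it. However, Section 3 places it before first product use, so it is a pre-treatment measurement, and the documents give no evidence that allocation affects it.

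**Conclusion.** The point holds, in limited form. The primary ANCOVA is not uniquely defined, DMI can be omitted, and age, although a stratification factor, is in no model. The cost of leaving out stratification factors is a somewhat conservative test and a little power: for age, about 0 to 2 points at assumed age differences of 0 to 0.6. The risk from open choice is a one-sided type I error of about 3 to 4.5% in place of 2.5%, only if the most favourable model were selected after unblinding.

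These sizes rest on assumed correlations and age effects, on normally distributed outcomes in place of a five-category rating, and on permuted blocks within strata. Assigning members of one household to the same group (Section 10) is not modelled. The documents do not support a claim that the sample size is wrong or that the secondary model is as open as the primary one.

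**What to change.** In Section 15, replace the optional wording and the generic formula with one model for Hypotheses 1 to 3, fixed before unblinding:

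*Y = group + DMI severity score + age stratum (≤54 / >54) + one named baseline MD item*

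State that the DMI score is the Visit 1 score with negatives set to 0, as used for the strata. Name the MD item, moistness or dryness, and make its use mandatory. For the two secondary endpoints, fit group, the same DMI and age terms, and the item's own baseline score, also as mandatory terms.

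**Cost.** A few sentences and one formula. All variables are already collected. With 135 completers, residual degrees of freedom go from 135 - 3 = 132 to 132 - 3 = 129. The sample size does not change. If none of the three covariates is prognostic, the price is only those three degrees of freedom.

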### Safety Analyses

Adverse events will be summarized overall and by treatment group.

## APPENDIX

### Advertising

Any advertisements used in recruitment of subjects must receive prior approval from P&G and the Investigator's IRB. A copy of the IRB-approved advertising and the documentation thereof must be provided to P&G.

### Data Collection

The Investigator has the responsibility for ensuring that all source documents (i.e., study and/or medical records) and CRFs are completed and maintained according to the study protocol and are available at the site.

### Case Report Forms

The Data Manager will supply the paper and/or electronic CRFs to be used in this study. It is the responsibility of the Investigator to maintain and submit accurate and timely CRFs to the Sponsor. All hard copy CRFs will be filled out legibly in ink.

All questions should be answered. For paper CRFs, if an entry requires correction, a single line will be placed through the entry so as not to obscure the original record, the corrected entry will be initialed and dated by the individual making the change, and a reason will be given for the change. There will be no whiteouts or erasures. For electronic CRFs, if an entry requires correction, the change is made directly to the CRF in the database, the user is prompted to provide a reason for the change, and the correction is logged in by an electronic audit trail.

As necessary, the Data Manager may make specified allowable changes to the database without issuing a query to the site, as agreed upon by study site per this protocol. Examples of allowable changes include incorrect date formats, incorrect current year recorded (as in the start of a new year), and unambiguous spelling errors. Changes to common abbreviations and symbols to equivalent text to meet system or coding constraints (e.g., @ = at, ~ = approximately), may also be allowable. Values that are ambiguous or open to interpretation will be queried to the sites. It is the responsibility of the Data Manager to ensure all changes are supported by information contained elsewhere and/or are unambiguous.

### Source Documents

The Investigator has the responsibility for ensuring that all source documents (i.e., study and/or medical records) and CRFs are completed and maintained according to the study protocol and is available at the site. Any CRF used as a source document must be identified as such in the Investigator Notebook.

### Protocol Amendments/Changes

Changes to the Protocol following IRB approval affecting the safety of subjects, scope or objectives of the investigation, or the scientific quality of the study will be documented as amendments. Such changes will require the Sponsor, Investigator, and IRB approval prior to implementation, unless immediate action is required to safeguard subject safety. Administrative or minor changes (e.g., typographical errors, changes in Sponsor personnel, etc.) will be documented as revisions but may not need to be submitted as amendments unless required by the IRB. Any change in the Sponsor's monitoring staff, Clinical Trial Manager or Medical Monitor during the conduct of the study, will be reported to the Investigator.

### Good Clinical Practices

This study is classified non-AMG, non-MPG according to German study classification but conducted in compliance with applicable sections of the US Federal Regulations governing informed consent (21 CFR 50) and IRBs (21 CFR 56). The conduct of this study will be in accordance with ICH-GCPs as published by the FDA, with the Commission Directive 2005/28/EC published by the European Union, and ISO 14155:2011. During the course of the trial, the clinical site will allow monitoring by the Sponsor (Clinical Trial Manager or designee) to check compliance with the Protocol, regulations and guidelines, adequacy of the equipment and facilities, and satisfactory data collection.

## **Institutional Review**

Prior to study initiation, the Investigator must obtain institutional review and approval of the Protocol, the consent form, and other necessary study-related documents in compliance with the US Code of Federal Regulations, Title 21, Part 56 or the ICH-GCPs Consolidated Guidelines, Chapter 3 and in compliance with Procter & Gamble SOP QS-CL-05 ("Institutional Review Board/Independent Ethics Committee Review and Approval"). The Investigator will maintain any original authorization letter(s) and will be available for review by the Sponsor. IRB approval letters should include the study title, Sponsor study number, the address of the IRB, date of request, and the signature of the IRB chairperson or designate. Additionally, the letter must acknowledge that both the Protocol and consent form have been approved by the IRB. The study will not begin until the Sponsor has received confirmation of IRB approval. The IRB shall also review the investigation at least once a year during study execution. The Investigator will notify the IRB when the study is terminated and provide confirmation that the study has been closed with the IRB to the Sponsor.

## **Investigator Final Report**

Following completion of the study, the Investigator shall submit a final report to the Sponsor describing the conduct of the study, deviations from planned conduct, early withdrawals and subject accountability, adverse events, and other information on study conduct. The Investigator's IRB may require more frequent status reports.

## **Records Retention**

The Investigator must retain the subject identification codes, informed consent documentation, clinical materials inventory, CRFs (paper or electronic media), medical records and other source data for a minimum of 2 years after the last regulatory approval has been received or the discontinuation of the study. The Investigator must receive written authorization from the Sponsor before destroying any study document. The Investigator will make the records available for inspection and copying upon the request of an authorized employee of a government authority or the Sponsor, at reasonable times. In the event the Investigator retires, relocates, or for any other reason withdraws from the responsibility for maintaining records for the period of time required, custody of the records may be transferred to another person who will accept responsibility for the records. Notice of such a transfer must be given in writing to the Sponsor.

The Research Participant's identification codes are a unique identifier assigned by the Principal Investigator to each trial subject to protect the Research Participant's identity and privacy. The identification codes are used in lieu of the Research Participant's name when the Principal Investigator reports all adverse events and other trial related data. These codes will be used on all study documents for the Research Participant's confidentiality (In order to protect the confidentiality of information concerning Research Participants, as stated in section 2.11 of the International Conference on Harmonization Good Clinical Practice: Consolidated Guideline (ICH-GCP).)

## **Serious Adverse Event Reporting**

A *serious adverse event* is defined as an event, which suggests a definite hazard or handicap to the subjects. Serious adverse events are any events resulting in death, life threatening situation, disability or permanent damage, hospitalization or prolongation of existing hospitalization, or congenital anomaly/birth defects; events requiring intervention to prevent permanent impairment/damage; or other serious (important) medical events.

When an Investigator is notified of a serious AE, the Investigator must promptly (within 24 hours) notify the Sponsor (Clinical Trial Manager or the Medical Monitor) of the serious or unexpected event, regardless of causality. Within 5 working days, a written and/or electronic report describing the circumstances of the event must be submitted to the Sponsor. The Investigator will be responsible for SAE reporting to the IRB.

**Study Medication Dispensing and Storage**

Study products will be stored in a secure area, under environmental condition as required by label instructions or as described in the Protocol and dispensed only under the authorization of the Investigator. The storage condition shall be properly documented. Both the receipt and dispensation of all test products (used and unused) will be documented using forms provided by the Sponsor or suitable forms provided by the site. Study products will be returned to the Sponsor following the trial, or alternatively, they will be destroyed at the clinical site provided the site has an existing SOP for the destruction of clinical materials and prior written approval from the Sponsor.

